7.10.1.3 Patient global assessment (PGA)

The self-reported patient global assessment (PGA) will be displayed by numbers and percentages by visit (after 1 year and, if sufficient data are available, after 2 years), treatment group and in total. A Chi-Square test for treatment comparison will be used.

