2.4 CONSORT flow diagram

The CONSORT flow diagram displays the number of randomized patients, patients included in the ITT population and PP population. This will be displayed overall and for each group (IG/CG) separately. For each group the reason and number of patients affected for exclusion from the ITT population and PP population will be presented.

3 Scope

The main analysis comprises the eCRF data and pharmacy claims data of prescribed medicinal products dispensed at community pharmacies from data processing centres (Apothekenrechenzentren) and health insurance funds (GKV/PKV) and data from health insurance funds about hospitalizations. The main analysis will be performed by the IZKS Mainz. The PDC will be determined by the pmv research group (University Cologne) and will be submitted to the IZKS Mainz for further analyses. Analyses regarding the intervention in participating pharmacies like analyses of drug-related problems (DRPs) and medication discrepancies are based on the eCRF and data documented during the intervention from pharmacists. These analyses will be performed by the Department of Medicine, ABDA, Berlin.

4 Study centers and study regions

In total, 258 patients have been recruited. 130 patients were randomized into the intervention and 128 in the control group. 110 patients from the intervention group and 127 patients from the control group could be included in the ITT population.

In total, 31 study centres (family physicians/GPs, internal medicine specialists, and both office- and hospital-based cardiologists) and 69 community pharmacies are taking part.

Pharmacies and physicians from nine different Federal States of Germany are taking part – that is, Baden-Württemberg, Bayern, Rheinland-Pfalz, Niedersachsen, Nordrhein-Westfalen, Saarland, Sachsen, Sachsen-Anhalt und Thüringen.

5 Variables

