5.8.3 Patient Global Assessment (PGA)

The PGA scale consists of a simple judgement indicating improvement, no change, or worsening since the start of the study and is documented after 12 months (visit 3) and at visit 5 (24 months) on a 7 point Likert scale (1="very much improved" to 4="unchanged" to 7="very much worsened").

The self-reported patient global assessment (PGA) will be displayed by numbers and percentages by visit (after 1 year and, if sufficient data are available, after 2 years), treatment group and in total.

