7.5.1 Demographics

All variables mentioned in chapter 5.3 will be tabulated.

Exploratory p-values of the Chi-Square test on differences between the treatment groups will be shown for categorical variables. They will be interpreted on a significance level of 5%.

Exploratory p-values of the t-test on differences between treatment groups assuming unequal variances will be shown for continuous variables. They will be interpreted on a significance level of 5%.

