7.10 Secondary analyses

All parameters will be tested for the ITT population on a two-sided level of significance 5%. All p-values will be interpreted in an exploratory way.

All secondary variables will also be analysed for the PP population. These analyses will be considered as exploratory only.

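### The seven-point ordered patient global assessment is compared by a chi-square test that ignores order: valid, but inefficient against a one-directional shift, and with no effect estimate planned

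*SAP*

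**What the plan says.** SAP 5.8.3 states that the PGA "is documented after 12 months (visit 3) and at visit 5 (24 months) on a 7 point Likert scale", running from 1 (best) through 4 (unchanged) to 7 (worst). The same sentence of the SAP also describes it more loosely: "The PGA scale consists of a simple judgement indicating improvement, no change, or worsening since the start of the study". No rule for reducing seven categories to three is given.

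For the analysis, SAP 7.10.1.3 plans a table of counts and percentages by visit and arm, and then: "A Chi-Square test for treatment comparison will be used". Protocol 11.4.3.3 says the same. Neither names a trend, Mantel-Haenszel or rank version, an effect estimate, a confidence interval, or an exact alternative for sparse cells.

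SAP 7.5.1 uses the same term as a general tool: "Exploratory p-values of the Chi-Square test on differences between the treatment groups will be shown for categorical variables". That supports reading it as the ordinary Pearson test. On the status of secondary results, SAP 7.10 states: "All p-values will be interpreted in an exploratory way". Protocol 11.1 confines the power claim to the primary efficacy variable.

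**The concern.** A Pearson test on a 2x7 table treats the seven categories as unordered labels. It spreads its sensitivity over 6 degrees of freedom, although the pattern of interest is that one arm sits further towards the improved end. The p-value is the same if the categories are shuffled.

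The choice also stands apart from the rest of the plan. The MLHFQ is analysed by ANCOVA with adjusted differences and confidence intervals (SAP 7.10.1.2), the PHQ-9 and self-estimated adherence by t-tests (7.10.1.4 and 7.10.1.5), and the primary PDC comparison by a stratified rank test (7.8). The PGA is the only patient-reported secondary scale whose order is discarded, and no reason is given.

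What is at stake is the reading of one patient-reported outcome. A non-significant result from an insensitive test, with no interval beside it, could be taken as showing that patients noticed no benefit.

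**Working it through.** **Figures in the plan.** No effect size, sample size or power is stated for the PGA, so there is no PGA figure to reproduce. The only powered figure is for the PDC. A two-sided t-test with difference 0.10, SD 0.22, alpha 5% and power 85% needs 87.9 per arm, so 88 per arm and N = 176. This agrees with SAP 1.2 and does not bear on the PGA.

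**Inputs from the documents.** Seven ordered categories (SAP 5.8.3); two-sided 5% level in the ITT population (SAP 7.10); 110 intervention and 127 control patients in the ITT population (SAP Table 2 and section 4). Missing values are not substituted (SAP 6.1), so 110 and 127 are upper limits.

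**Assumptions not in the documents.** The control category shares, the size of the shift and the number of patients with PGA data.

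**Step 1: degrees of freedom alone.** Power = P(noncentral chi-square with df and noncentrality λ exceeds the 95% point of the central chi-square with df).

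- 1 df, 80% power: λ = (1.960 + 0.842)² = 7.85.
- 6 df at λ = 7.85: power 52.1%.
- 2 df (three levels) at λ = 7.85: power 70.9%.
- 80% power on 6 df needs 1.74 times that λ, hence about 1.74 times the patients.

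This step needs no category shares, but it takes λ as equal across the tests. Step 2 checks that by simulation.

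**Step 2: simulation.** Four assumed control distributions for categories 1 to 7, in percent:

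- symmetric: 3, 10, 20, 34, 20, 10, 3
- centre-heavy: 2, 6, 17, 50, 17, 6, 2
- flat: one seventh each
- skewed to worse: 2, 6, 12, 35, 25, 15, 5

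The intervention arm follows proportional odds: each cumulative odds in the control arm is multiplied by the common odds ratio (OR). There were 2,000 trials per scenario (Monte Carlo standard error about 1 point). The tests were the Pearson 2x7 chi-square, the tie-corrected Wilcoxon rank-sum, and the chi-square after collapsing to improved, unchanged and worse. Rejection rates at 110/127, as the range over the four distributions:

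| Common OR | Wilcoxon | Chi-square 2x7 | Chi-square, 3 levels |
|---|---|---|---|
| 1.0 | 4.5-6.0% | 4.6-5.2% | 4.1-5.8% |
| 1.5 | 40-43% | 18-22% | 30-31% |
| 1.75 | 65-69% | 36-39% | 51-55% |
| 2.0 | 80-86% | 51-59% | 70-72% |
| 2.5 | 97-98% | 82-86% | 91-94% |

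A repeat simulation at OR 2.0 gave 82-86% for Wilcoxon and 55-60% for chi-square. The conclusions use the wider ranges: 51-60% for chi-square at OR 2.0, and 96-98% for Wilcoxon at OR 2.5.

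With an assumed 80 and 100 patients providing PGA data, OR 2.0 gives 71-74% for Wilcoxon and 39-44% for chi-square. Fewer patients lower both.

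**The case against.** The strongest reply is that little depends on this test. The PGA is secondary, its p-value is exploratory and the trial was never powered for it. The chi-square test holds its level, introduces no bias and leaves the primary analysis untouched. Protocol and SAP agree with each other. All of this stands, and it limits the point to one of efficiency.

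The reading of the test is also an inference. The term is unqualified, and a row-mean-score or trend chi-square would use the order. The three-way description in SAP 5.8.3 might hint at a 2-df table. Empty end categories would also reduce the degrees of freedom: five occupied categories give 60% at the noncentrality of step 1. Even so, the text names neither an ordinal version nor a collapsing rule, and the three-level test still falls short of the rank test in every shifted scenario run.

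The calculations assume a one-directional, proportional-odds shift. For a non-monotone difference, with more patients at both ends for instance, the general chi-square can do better. That is a real cost of switching.

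A reader might infer three stronger things that the documents do not support:

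- **That a significant result would not show which arm did better.** The planned table by arm lets the reader see the direction of a one-directional shift. What is missing is an estimate with an interval.
- **That a real benefit would probably be missed.** This depends on the effect. At OR 2.5 and full ITT size the chi-square detects it in 82-86% of trials. At OR 1.5 the rank test also misses it more often than not.
- **That sparse cells undermine the test.** An expected count falls below 5 in the smaller arm when the pooled share of a category is under 5/110 = 4.5%. The documents give no PGA distribution. At OR 2.0 and 110/127, the share of simulated trials with such a cell was about 100%, 69% or 16% when each end category held an assumed 2%, 5% or 8% of controls.

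**Conclusion.** The point holds as an efficiency improvement to a secondary, exploratory analysis. As written, the plan most naturally means a Pearson 2x7 test that ignores the order of the scale and comes without an effect estimate. Against a one-directional shift, the loss on degrees of freedom alone is from 80% to 52% power. In the simulations at 110/127 it is about 19 to 30 percentage points for odds ratios from 1.5 to 2.0, and 11 to 15 points at 2.5, where the rank test is near its ceiling.

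The simulated sizes rest on assumed category shares, proportional odds and complete PGA data in the ITT population. The direction of the loss was the same in every shifted scenario tried. The trial's primary conclusions are not affected.

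**What to change.** In SAP 7.10.1.3 and Protocol 11.4.3.3, replace the chi-square test with either a Wilcoxon rank-sum test or a proportional-odds model that reports a common odds ratio with 95% CI. The model has the advantage of supplying the missing estimate. Keep the table of categories by arm and visit as description; it would still show a non-monotone difference, to which the new test is less sensitive. If an ordinal form of the chi-square was meant all along, naming it would settle the test, and an estimate with an interval should still be added.

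The cost is one sentence in each document and no new data. The SAP already uses a rank-based procedure for the PDC in section 7.8. The change should be made before PGA results by arm are seen. If they have been seen, the ordinal analysis should be reported beside the planned test and labelled as added later.

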7.10.1.4 PHQ-9

The PHQ-9 total score and the changes to baseline will be analysed descriptively by visit (after 1 year and, if sufficient data are available, after 2 years), treatment group and in total. T-tests for comparing treatment groups will be performed.

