### 11.4.3.4 PHQ-9

The PHQ-9 total score and the changes to baseline will be analysed descriptively by visit (after 1 year and, if sufficient data are available, after 2 years) for each treatment group and in total. t-tests for comparing treatment groups will be performed.

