1.4 Randomization

Eligible patients are assigned in a 1:1 ratio to the intervention or control group. Minimization with 20% residual randomness is used to ensure balance of the following characteristics: Gender (male/female), age (≤ 75 , > 75), NYHA functional class (I and II, III and IV), PHQ-9 (score < 10 , ≥ 10), diabetes mellitus (yes/no), study region (according to regional Associations of Statutory Health Insurance Physicians (KV-Region)).

A web-based randomization tool developed by IZKS Mainz is used within this study allowing investigators to randomize patients via a secure web interface.

Subjects withdrawn from the study retain their identification codes (i.e. patient number). New subjects must always be allotted a new identification code.

2 Analysis populations

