5.8.4 Patient Health Questionnaire (PHQ-9)

Change in depression measure by the Patient Health Questionnaire (PHQ-9D = validated German version of the PHQ-9) between baseline and 365 days (main secondary outcome) and between baseline and 730 days (other secondary outcome). The PHQ-9D will be filled out at screening, visit 3 (after 12 months) and visit 5 (after 24 months). The PHQ-9D is a self-administered version of the PRIME-MD diagnostic instrument common mental disorders. The PHQ-9 is the depression module, which scores each of the 9 DSM-IV criteria. It has been validated for use in primary care. The PHQ-9D questionnaire will be analysed by assigning 0 point for the category “never”, 1 point for the category “at some days”, 2 points for the category “at more than 50% of the days” and 3 points for the category “nearly every day”. The total score will be calculated building the sum of all items and therefore ranges between 0 and 27. The cut-off for signs of depression was set at a PHQ-9 score of ≥ 10 .

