5.8.5 Self-estimated adherence

The self-estimated adherence is documented at visit 1, 3, and 5 on a scale from 0 to 100 percent in 5 % steps and absolute values by visit and changes will be analysed between baseline and visit 3, and visit 5, respectively.

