7.10.1.2 Quality of life (Minnesota Living with Heart Failure Questionnaire, total score)

The changes to baseline of the total score of the Minnesota Living with Heart Failure Questionnaire after 1 year and, if sufficient data are available, after 2 years will be analysed by an ANCOVA, including treatment as fixed effect and total score at baseline as covariate. Parameter estimates and adjusted mean differences (LSMEAN differences) will be shown together with their corresponding p-values and 95% confidence intervals.

Additionally, the total score as well as the corresponding change to baseline will be analysed descriptively by visit, treatment group and in total.

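### PHQ-9 and self-estimated adherence are compared by t-tests without baseline adjustment, although baselines are collected and MLHFQ gets a baseline-adjusted ANCOVA; the tests are valid but less precise

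*SAP*

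**What the plan says.** **PHQ-9.** SAP 7.10.1.4 describes the total score and its change from baseline by visit, then adds "T-tests for comparing treatment groups will be performed". Protocol 11.4.3.4 agrees: "t-tests for comparing treatment groups will be performed". SAP 5.8.4 defines the outcome as change, ranks the change to 365 days as the main secondary outcome and the change to 730 days as an other secondary outcome.

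**Self-estimated adherence.** SAP 7.10.1.5 and Protocol 11.4.3.5 also plan t-tests and do not mention change. SAP 5.8.5 says that "The self-estimated adherence is documented at visit 1, 3, and 5"; it plans to look at visit values, and "changes will be analysed between baseline and visit 3, and visit 5, respectively". It does not rank the two forms.

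**MLHFQ.** On the same visit schedule (Table 1 in both documents), the change in total score "will be analysed by an ANCOVA, including treatment as fixed effect and total score at baseline as covariate" (SAP 7.10.1.2; likewise Protocol 11.4.3.2). Adjusted mean differences and 95% confidence intervals are to be reported.

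**Status.** SAP 7.10 tests secondary outcomes at a two-sided 5% level and treats all their p-values as exploratory. Protocol 11.1 powers the trial for the primary efficacy variable only.

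**The concern.** Three patient-reported outcomes share one schedule and have a baseline value. One is adjusted for baseline and two are not, and no reason is given. SAP 5.8.2 and 5.8.4 even give MLHFQ and PHQ-9 the same definition and rank: change to 365 days, main secondary outcome.

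The cost is precision. A t-test on the follow-up value ignores the baseline. A t-test on change subtracts it with a fixed weight of one, which is too much when the correlation between visits is below one (with equal SDs). A chance difference at baseline is therefore left uncorrected by the first test and over-corrected by the second. Balance at baseline is also only partly protected. PHQ-9 enters the minimization in two classes only, self-estimated adherence does not enter it, and 20 intervention patients but only 1 control patient leave the ITT set after randomization (SAP Table 2).

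For self-estimated adherence there is a second, smaller issue. Visit value and change are both named, the test is not tied to either, and the two can give different answers.

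**Working it through.** **The plan's own figure.** The documents state no power or precision for these two outcomes. The only planning figure is for PDC: a difference of 0.10, SD 0.22, two-sided t-test at 5%, 85% power (SAP 1.2). This gives 87.9, so 88 per group, and it reproduces. It has no bearing on PHQ-9 or self-estimated adherence.

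**Inputs from the documents.**
- t-tests with no covariate: SAP 7.10.1.4 and 7.10.1.5.
- Baseline collected at V1: SAP Table 1, 5.8.4 and 5.8.5.
- ITT groups of 110 and 127: SAP Table 2.
- Two-sided 5%: SAP 7.10.

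**Assumptions, not in the documents.**
- Equal SDs at baseline and follow-up.
- Baseline to follow-up correlation r between 0.3 and 0.7.
- For the power illustration only, a true difference of 0.3 SD.

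**Step 1: variance of the treatment difference, relative to a t-test on the follow-up score.**
- Follow-up t-test: 1
- Change t-test: 2(1 − r)
- ANCOVA: 1 − r²

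The ratio of ANCOVA to the follow-up t-test is 1 − r². The ratio of ANCOVA to the change t-test is (1 − r²) / (2(1 − r)) = (1 + r)/2. Both are below 1 for 0 < |r| < 1, so in large samples ANCOVA is more precise than either t-test.

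**Step 2: numbers.**

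| | r = 0.3 | r = 0.5 | r = 0.7 |
|---|---|---|---|
| Variance, follow-up t-test | 1.00 | 1.00 | 1.00 |
| Variance, change t-test | 1.40 | 1.00 | 0.60 |
| Variance, ANCOVA | 0.91 | 0.75 | 0.51 |
| Reduction against follow-up | 9% | 25% | 49% |
| Reduction against change | 35% | 25% | 15% |
| Patients needed relative to ANCOVA, follow-up | 1.10 | 1.33 | 1.96 |
| Patients needed relative to ANCOVA, change | 1.54 | 1.33 | 1.18 |

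The advantage over the follow-up t-test vanishes as r approaches 0, and the advantage over the change t-test vanishes as r approaches 1.

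**Step 3: illustration of power.** With v the relative variance from step 1, the standard error in SD units is √(1/110 + 1/127) × √v = 0.1302 × √v, and power is Φ(0.3 / (0.1302√v) − 1.96).

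| | r = 0.3 | r = 0.5 | r = 0.7 |
|---|---|---|---|
| Follow-up t-test | 63% | 63% | 63% |
| Change t-test | 50% | 63% | 84% |
| ANCOVA | 68% | 76% | 90% |

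Fewer patients than the ITT numbers will have a 12-month questionnaire, so the power levels are optimistic. The variance ratios do not depend on the number of patients.

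**Step 4: score or change.** Change is follow-up minus baseline. With the baseline in the model, ANCOVA on the score and ANCOVA on the change give the same treatment estimate and standard error. One ANCOVA therefore removes the open choice for self-estimated adherence.

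**The case against.** The strongest reply is that nothing is wrong. Under randomization both kinds of t-test are valid, the p-values are exploratory, and no decision rests on these outcomes. That stands and sets the weight of the point. It does not remove the gain: exploratory results are read through estimates and intervals, which is where adjustment helps.

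Second, the size of the gain rests on a correlation that the documents do not give, applied to two different instruments. That also stands, and is why a range is shown. The direction does not depend on the value chosen.

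Third, PHQ-9 class is a minimization factor, which limits imbalance. This is partly right, but it covers two classes of one outcome only, and a test that ignores a balanced prognostic factor tends to be conservative. The plan's reason for not adjusting for stratification factors (Protocol 11.4.1, SAP 7.10.2) concerns the primary efficacy and recurrent-event analyses.

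Fourth, the protocol specifies these t-tests, so removing them would be more than a SAP edit. That is correct, and the fix allows for it.

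A reader might also infer three stronger points that the documents do not support:

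- **That score and change are both tested, with no rule for which counts.** SAP 7.10.1.4 and 7.10.1.5 do not say which quantity is tested. For PHQ-9, SAP 5.8.4 names change to 365 days. Only self-estimated adherence has two unranked forms.
- **That a comparison with 80% power would rise to 90–94%.** That holds only against a follow-up t-test, with r of 0.5 to 0.6: Φ(2.80/√0.75 − 1.96) = 90% and Φ(2.80/√0.64 − 1.96) = 94%. Against the change t-test the ratios are 0.75 and 0.80, which give 90% and 88%. At r = 0.3 against follow-up it is about 84%. No comparison planned at 80% power exists for either outcome.
- **That the t-tests are biased by design.** They are not. Regression to the mean matters here only if baselines differ. Differences created by the ITT exclusions are a separate matter, which baseline adjustment does not cure.

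**Conclusion.** The point holds as one of efficiency and consistency. The t-tests are valid, but for both outcomes a baseline already collected goes unused as a covariate, while MLHFQ is adjusted. Assuming equal SDs and r of 0.3 to 0.7, ANCOVA lowers the variance by 9% to 49% against a follow-up t-test and by 35% to 15% against a change t-test. For PHQ-9 the change comparison applies, so the expected reduction is 15% to 35%. For self-estimated adherence either may apply, because the plan leaves the form open. The change is worth making because it costs almost nothing. It affects no primary result, and the findings remain exploratory.

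**What to change.** In SAP 7.10.1.4 and 7.10.1.5, make the treatment comparison at 1 year, and at 2 years if data suffice, an ANCOVA with treatment as fixed effect and the baseline value of the same measure as covariate. Report the adjusted mean difference with its 95% CI and p-value, as SAP 7.10.1.2 does for MLHFQ. Keep the t-tests as supportive analyses, or align Protocol 11.4.3.4 and 11.4.3.5 with the SAP. Make the change before results by group are seen.

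Self-estimated adherence is bounded at 0–100% and recorded in 5% steps, so a rank-based or robust check could be added; the boundedness affects the t-test equally.

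Cost: a few sentences, the MLHFQ program reused, and no new data. The one downside is that patients without a baseline value drop out of the ANCOVA, since SAP 6.1 plans no substitution of missing values. They drop out of a change t-test as well. For PHQ-9 such patients should be few, because its class is needed for the minimization.
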